### 3.3 Study medications

Articaine Sterile Topical Ophthalmic Solution (AG-920) [REDACTED]

The comparator product, 0.5% Proparacaine Hydrochloride (NDC number 24208-0730-06, manufactured by Bausch & Lomb), is packaged in 15 mL dropper bottles.

**Figure 2: Investigational Medicinal Product**

	INVESTIGATIONAL PRODUCT	
PRODUCT NAME	Articaine Sterile Topical Ophthalmic Solution (AG-920)	Proparacaine HCl Ophthalmic Solution, 0.5%
ACTIVE INGREDIENT	Articaine Hydrochloride	Proparacaine HCl
INACTIVE INGREDIENTS	[REDACTED]	Glycerin Purified water Benzalkonium chloride 0.01%
UNIT DOSE	[REDACTED]	15 mL dropper bottle
ROUTE OF ADMINISTRATION	Topical ocular	Topical ocular
DOSING REGIMEN	2 drops 30 seconds apart from a single vial into study eye	2 drops 30 seconds apart from a single bottle into study eye
STORAGE REQUIREMENTS	[REDACTED]	Store bottles under refrigeration at 2° to 8°C (36° to 46°F)

#### 3.3.1 IMP Packaging and labeling

Investigational Medicinal Product (IMP) will be packaged with an investigational label. Marketed Proparacaine HCl Ophthalmic Solution will be “overwrapped” with an investigational label.

The container-closure system to be used for the AG-920 in this clinical study [REDACTED] vial. [REDACTED]

Each foil pouch will be labeled with an investigational label with the following minimal

information: the study number, kit number, and storage statement, including a statement “Caution – New Drug – Limited by Federal (US) Law to Investigational Use” or equivalent. Each foil pouch will be individually placed into a single-unit carton and a similar investigational label will be applied to the carton.

The comparator product, 0.5% Proparacaine Hydrochloride [REDACTED], is packaged [REDACTED]. The bottles will be stored in a kit comprised of an individually labeled carton containing 1 bottle. [REDACTED]

[REDACTED] Each kit will be labeled with an investigational label with the following minimal information: the study number, kit number, and storage statement, including a statement “Caution – New Drug – Limited by Federal (US) Law to Investigational Use” or equivalent.

### 3.3.2 Storage of study medication

[REDACTED]

The Proparacaine should be stored refrigerated (2 – 8°C or 36 – 46°F).

Prior to administering to the subject, all investigational material must be stored in a secure location with strictly limited access documented by signature of authorized persons who may dispense investigational materials.

### 3.3.3 Study medication accountability

Accountability of IMP kits and comparator bottles will be conducted by a member of the site and verified by a study monitor. Accountability will be completed by performing reconciliation between the number of kits sent to the site and the amount used and unused at the time of reconciliation. Site staff will be queried about any discrepancies.

IMP kit shipment records will be verified, and accountability performed by comparing the shipment inventory sheet to the actual quantity of kits received at the site. In addition, receipt of kits will be confirmed by the study monitor. Accurate records of receipt and disposition of the kits (e.g., dates, quantity, subject number, kits used, kits unused, etc.) must be maintained by the Investigator or his/her designee.

At the end of the study and after the monitor has verified kit and bottle accountability, all IMP is to be returned to American Genomics (or designee) or destroyed at the site and documented per the site’s standard process.

### 3.4 Expected duration of subject participation

Each subject is planned to participate in the study for up to 2 Visits (Screening and Treatment/Eye Exam) and a Follow-up Phone Call 1-4 days following Visit 2 (Day 2-5).

### 3.5 Randomization and procedure for breaking the code

A randomization code for allocating the treatments and study eye will be prepared by an independent biostatistician, who is not involved in the day-to-day conduct of the study. Subjects

will be randomized in a 1:1 ratio to receive AG-920 or Proparacaine HCl Ophthalmic Solution. The site will have a randomization list that will assign each subject to treatment and study eye.

The study is single masked. Treatment assignments will be masked to the subjects and their parent/legal guardian only so there is no reason to break the code.

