### 4.1 Subject inclusion criteria

1. Male or female aged 10 years or less (pre-pubescent with no childbearing potential)
2. Capable of undergoing an eye exam per investigator judgement
3. Subject's legally appointed and authorized representative willing to sign and date an informed consent form (ICF) and, where appropriate, the subject willing to sign an assent form prior to any study-related procedures being performed.
4. Parent/legal guardian and subject are willing and able to follow instructions and can be present for the required study visits and Follow-up Phone Call for the duration of the study.
5. Have a healthy, normal cornea.
6. Have a planned ophthalmic examination.

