### 4.2 Subject exclusion criteria

Subjects who meet any of the following exclusion criteria are ineligible for this study:

1. Have participated in an investigational study (drug or device) within the past 30 days.

2. Have a known contraindication to local anesthetics, Septocaine®, any component of the Investigational Medical Product (IMP) or Proparacaine HCl Ophthalmic Solution.
3. Children with known autism spectrum disorders or known to have heightened sensitivity.
4. Corneal pathology that would make the corneal sensitivity lower/higher or make the test hard to perform or interpret (e.g., central corneal scar, clinically apparent corneal edema, etc.).
5. Have low visual acuity  
(Optotype capable): Corrected acuity in either eye worse than 20/200 Snellen (0.1 ETDRS) or equivalent  
(Not optotype capable): No demonstrable reaction to light.
6. Manifest nystagmus
7. Have had ocular surgery (intraocular, refractive, extraocular muscles, eyelid) or general surgery in either eye within the past 45 days (Note: dental restorative work allowed).
8. Have had an intravitreal injection in either eye within 14 days of randomization.
9. Have ocular surface disease requiring punctal plugs, or evidence of current ocular inflammation.
10. Subject who must wear contact lenses on Study Day 1 (Visit 2).
11. Are currently using, or used within the past 7 days, a systemic or topical Non-steroidal Anti-Inflammatory Drug (NSAID).
12. Are currently using, or used within the past 30 days, a systemic opioid or opiate analgesic.
13. The subject's parent(s) or legal guardian(s) is a study team member (i.e., has direct involvement in this study or other studies under the direction of the Investigator or the study center) or is a family member of either the Investigator or other team members.

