##### 6.4.2 IMP Treatment

- Once qualification is confirmed, subject will be randomized.
  - Subject will be randomly assigned to receive a single dose of either AG-920 or Proparacaine HCl Ophthalmic Solution
  - Subject will be randomly assigned to receive the IMP dose into one eye (OD or OS) only (study eye)
  - Subjects and parent/legal guardian should be reminded that instillation of study drug, like other topical anesthetic drops, may cause a mild stinging or burning sensation upon instillation.
- Retrieve IMP kit number assigned and confirm study eye.
- For AG-920:
  - [REDACTED]
  - Administer 1 drop of IMP to the study eye
    - Wait 30 seconds
    - Administer a second drop of IMP to the same study eye from the same vial

- [REDACTED]
- For Proparacaine:
  - Remove dropper bottle from kit (carton)
  - Open bottle top
  - Administer 1 drop of IMP to the study eye
  - Wait 30 seconds
  - Administer a second drop of IMP to the same study eye from the same vial
  - Recap bottle and retain used bottle in the carton (kit) for accountability
- Assess for adverse events

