### 2.4 Randomization

As stated in the protocol, a randomization schedule generated by the Sponsor or designee will be used to assign subjects to each of the two treatment groups with a 1:1 allocation ratio to receive a single dose of AG-920 or Proparacaine according to the randomization schedule.

Study medication will be packaged with an investigational label. Marketed Proparacaine HCl Ophthalmic Solution will be "overwrapped" with an investigational label.

[REDACTED]

[REDACTED]

[REDACTED]

Each eligible subject will be assigned to one of the prepackaged packs available at a site. The study is single masked. Treatment assignments and study medication will be masked to the subjects and their parent/legal guardian only. The treatment randomization number or study medication kit number assigned to the subject will be recorded on the CRF at the site.

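### Protocol 3.5 puts a randomization list at the site and describes no step that hides the next assignment from whoever judges eligibility, so enrolment could be selective by arm

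*Protocol*

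**What the plan says.** **The list.** Protocol 3.5 has the code "prepared by an independent biostatistician, who is not involved in the day-to-day conduct of the study". It then says: "The site will have a randomization list that will assign each subject to treatment and study eye". This section is not redacted.

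**Masking.** Protocol 3.5: "Treatment assignments will be masked to the subjects and their parent/legal guardian only so there is no reason to break the code". SAP 2.4 agrees: "Treatment assignments and study medication will be masked to the subjects and their parent/legal guardian only". The investigator and site staff are therefore not masked.

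**Order of steps.** Protocol 6.4.2: "Once qualification is confirmed, subject will be randomized"; the assigned kit is then retrieved. SAP 2.4: "Each eligible subject will be assigned to one of the prepackaged packs available at a site". Several lines just before that SAP sentence are redacted.

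**Criteria that leave discretion.** Inclusion 2 (Protocol 4.1) is "Capable of undergoing an eye exam per investigator judgement". Exclusion 3 (Protocol 4.2) is "Children with known autism spectrum disorders or known to have heightened sensitivity", with the sensitivity undefined. Exclusion 4 covers corneal pathology, including pathology that would make the test difficult to do or read.

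**Rescreening and timing.** Protocol 6.2 lets a screen failure return once, 7-30 days later. Protocol 6.3 allows screening and dosing on the same day.

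**Endpoint.** The principal investigator answers yes or no on whether anesthesia was adequate for the exam (SAP 2.6). There is no secondary efficacy endpoint (SAP 2.6.2).

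**The concern.** Randomization protects against selection bias only if the person accepting a child cannot foresee the assignment. An independent statistician protects how the sequence is made. That does not protect the sequence once a list is at the site and the staff are unmasked. Allocation can be concealed even in a fully open-label trial, so the choice of single masking does not settle this point.

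The discretion matters because inclusion 2 asks nearly the same question as the primary endpoint: can this child be examined? If a child expected to be difficult is accepted under one product and failed or deferred under the other, the arms differ in examinability before any drop is given. Every child so enrolled is properly in the ITT set, and study-eye side, the only adjustment in SAP 2.9.1, is unrelated to the selection. The result could move toward or away from the equivalence claim whatever the drugs do.

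**Working it through.** The plan gives no figure to reproduce on this point. The sample size (up to 70 enrolled for at least 60 evaluable, about 30 per arm) is stated as directed by the FDA and not derived. The check has three parts.

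**1. How much of the sequence can be foreseen**

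Share of next assignments guessed correctly by someone who sees past ones:
- List open at the site: 100%.
- Concealed, simple 1:1 randomization: 50%.
- Concealed, known fixed blocks of 2: (0.5 + 1)/2 = 75%.
- Concealed, known fixed blocks of 4: (0.5 + 2/3 + 2/3 + 1)/4 = 70.8%.
- Concealed, known fixed blocks of 6, by full enumeration: 68.3%.

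The readable text gives no block size. Concealment removes certainty, but unmasked staff could still guess well if blocks were short and fixed.

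**2. Shift per steered child, arm of 30**

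- Upper bound, a certain failure replaced by a certain success: 1/30 = 3.3 points.
- Illustration (assumed): 30% of children are hard to examine; response is 50% in them and 95% in the rest, on either drug. The average child responds at 0.30 × 0.50 + 0.70 × 0.95 = 0.815. Replacing one hard child by an average child moves the arm by (0.815 − 0.50)/30 = 0.0105, or 1.05 points.

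If a share s of hard children is turned away whenever AG-920 is next, the hard share in that arm becomes 0.30(1 − s)/(1 − 0.30s). With equal drugs the false advantage for AG-920 is:

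| s | AG-920 | Proparacaine | Difference | Children turned away |
|---|---|---|---|---|
| 0.25 | 84.1% | 81.5% | 2.6 points | 30/0.925 − 30 = 2.4 |
| 0.50 | 87.1% | 81.5% | 5.6 points | 30/0.85 − 30 = 5.3 |
| 1.00 | 95.0% | 81.5% | 13.5 points | 30/0.70 − 30 = 12.9 |

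**3. Effect on the plan's decision rules if AG-920 is truly worse**

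Exact binomial enumeration, 30 per arm. The rules are the chi-square P > 0.05 of Protocol 9.4.6 and the 90% CI within ±20% of SAP 2.9.1, with ±20% read as percentage points and eye side ignored. Assumed: 30% hard children; 95% response on either drug in the others; in hard children, 95% on proparacaine and 35% on AG-920. With no steering, AG-920 is 0.30 × 0.35 + 0.70 × 0.95 = 77.0% against 95.0%.

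| s | Apparent difference | 90% CI rule met | P > 0.05 |
|---|---|---|---|
| 0 | −18.0 points | 10.7% | 43.6% |
| 0.50 | −10.6 points | 38.3% | 71.5% |
| 1.00 | 0 | 92.0% | 97.2% |

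With 50% instead of 35% for AG-920 in hard children, the true difference is −13.5 points. The CI rule is then met 24.5%, 53.6% and 92.0% of the time, and P > 0.05 occurs 60.4%, 80.8% and 97.2% of the time, at the same three values of s.

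**The case against.** The strongest reply is that the text shows less than a reader might infer.

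- **That the site holds the complete list and the investigator knows each assignment in advance.** Protocol 3.5 does not say who at the site holds the list or whether lines are revealed one at a time. What stands is that nothing readable prevents the next line from being read. Confirming eligibility first fixes the order of steps but hides nothing on a list already there.
- **That eligibility is subjective as a whole.** It is not. Age, acuity, recent surgery, injections, and NSAID and opioid use are objective. The discretion lies in inclusion 2 and exclusions 3 and 4, and exclusion 3 is worded as known history.
- **That the kits reveal the assignment.** The documents do not support this. Protocol 3.3.1 puts both products in labelled cartons, and the listed minimum label content has no product name. Whether the storage statements differ cannot be checked, because AG-920 storage is redacted.
- **That a few steered children would decide the result.** Three children move an arm by 10 points only if each swap turns a certain failure into a certain success. Under the illustration they move it by 3 × 1.05 = 3.2 points. A shift in a point estimate is also not directly comparable with a rule applied to a confidence interval.

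Two further points are fair. The redacted lines in SAP 2.4 could describe release of assignments, though they cannot be presumed to reverse an explicit sentence in the protocol. Selective failing would also leave a record: exclusion reasons are captured (Protocol 10.4), screening is summarized by site (SAP 3.2) and eligibility checks are listed (SAP 10). A record helps detection afterwards; it does not conceal anything or repair the comparison.

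**Conclusion.** The concern holds as a gap in allocation concealment. The protocol places a list giving treatment and study eye at the site, the staff are unmasked, no concealing step is described, and a few criteria leave discretion tied to the endpoint. Selection by arm is possible, and the analysis could not remove it.

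The documents do not show that anyone would steer enrolment, so this is opportunity and not demonstrated bias. The firm bound is 3.3 points per child in an arm of 30. The figure of about 1 point, and both tables, rest on assumed proportions and response rates that the documents do not give. Complete steering would mean turning away about 13 children in the illustration, so the last row of each table is an extreme. Lesser steering can still push toward an equivalence claim when AG-920 is worse. The point should be settled before the first child is enrolled, because it cannot be repaired afterwards.

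That the unmasked investigator also rates the endpoint is a separate matter, which concealing the list would not cure.

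**What to change.** Amend Protocol 3.5 so that:

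- the list stays with the independent statistician and is not held at the site;
- the site receives one assignment (treatment and study eye) at a time, by EDC release or from sequentially numbered opaque sealed envelopes, only after that child's eligibility has been recorded and locked;
- the times of eligibility lock and of release are both logged;
- if blocks are used, their sizes vary and are not disclosed to the site, because staff see past assignments.

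Align SAP 2.4 with this, first checking whether its redacted lines already describe release.

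The cost is small: EDC set-up (the documents describe the system for data capture, not for randomization) or about 70 envelopes at 1-3 sites, plus the time to keep the log. Sample size, visits and treatment do not change.

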## **5 TREATMENT OF SUBJECTS**

Subjects will receive a single dose (two drops) of IMP in one (study) eye. The IMP will be randomized as either AG-920 or Proparacaine HCl Ophthalmic Solution. The study eye will be randomized as either right eye (OD) or left eye (OS). The single dose will be administered by the clinic staff.

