## 7 ASSESSMENT OF EFFICACY

Assessments of efficacy will be a determination by the investigator as to whether there was adequate local anesthetic effect to perform the eye exam for which the subject is seeing the ophthalmologist.

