## **2.6 Efficacy and Safety Measurements**

In this study, primary efficacy endpoint will be assessed using the proportion of subjects with adequate local anesthetic effect assessed by the principal investigator (PI) so that the eye exam for which the subject is seeing the ophthalmologist can be conducted.

Two to four minutes following treatment of study medication, the PI will be asked "Did you achieve adequate anesthesia to conduct the eye exam?" The PI's response is recorded as "YES" for adequate anesthesia or "NO" for inadequate anesthesia.

Safety will be assessed through subject early terminations, adverse events, visual acuity, and external eye exam, and concomitant medications. Slit lamp bio-microscopy test will be conducted if needed (if an AE is suspected).

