### **2.6.2 Secondary efficacy measure**

No secondary efficacy endpoint is defined in this study.

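### The only efficacy outcome is a subjective yes/no from an investigator whom neither document masks, in a trial that claims equivalence when it finds no difference, and the Protocol and SAP disagree on who gives the drops

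*Protocol*

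**What the plan says.** **Outcome.** Protocol section 7 states: "Assessments of efficacy will be a determination by the investigator as to whether there was adequate local anesthetic effect to perform the eye exam". SAP 2.6 turns this into one question to the principal investigator, "Did you achieve adequate anesthesia to conduct the eye exam", answered YES or NO at 2-4 minutes after dosing. SAP 2.6.2 adds: "No secondary efficacy endpoint is defined in this study". The visible text gives no criteria for adequacy. Part of the investigator query in Protocol 6.4.3.1 is redacted.

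**Masking.** Protocol 3.5 says: "Treatment assignments will be masked to the subjects and their parent/legal guardian only so there is no reason to break the code". SAP 2.4 agrees: "Treatment assignments and study medication will be masked to the subjects and their parent/legal guardian only". Protocol 3.5 also puts the allocation at the site: "The site will have a randomization list that will assign each subject to treatment and study eye". Protocol Figure 2 and sections 3.3.1 and 6.4.2 show different containers, a vial for AG-920 and a 15 mL dropper bottle for Proparacaine.

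**Who doses.** Protocol section 5 says: "The single dose will be administered by the clinic staff". The Protocol Summary agrees, and Protocol 3.1 names study staff. SAP 2.2 instead has the principal investigator give the medication and perform the exam.

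**Decision rule.** Protocol 9.4.6 claims equivalence if the difference is near zero and P > 0.05, with no margin. SAP 2.9.1 keeps the P > 0.05 logic and adds a rule that the 90% CI of the difference lie within ±20% of the reference treatment.

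**The concern.** The people who are masked, the child and the parent, do not supply the endpoint. The person who supplies it is not masked.

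In a superiority trial, indiscriminate generosity in scoring usually works against the sponsor. Here the favourable conclusion is the absence of a difference, so an assessor who gives AG-920 the benefit of the doubt moves the data towards the claim. An assessor who is sceptical of the new product moves them away from it and could cost AG-920 a deserved claim. The per-protocol, by-site and subgroup analyses all reuse the same answer, so none of them can reveal the bias or correct it.

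**Working it through.** **No figure in the plan to reproduce.** Protocol 9.2 says the sample size was set by regulatory direction and not by calculation. It gives no response rate or power. The check therefore asks how sensitive the two decision rules are to a few answers.

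**Inputs from the documents.** About 30 evaluable children per arm (Protocol Summary); two-sided 0.05 level and Pearson chi-square (Protocol 9.4.1, 9.4.6); 90% CI from an ANOVA, and the ±20% rule (SAP 2.9.1).

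**Assumptions.** True success rates; the share L of true AG-920 failures scored YES; study-eye factor ignored; no continuity correction.

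**Formulas.**
- Observed AG-920 rate: q = p + L(1 − p).
- Pooled variance: s² = [30·a(1−a) + 30·c(1−c)]/58, where a and c are the observed proportions for AG-920 and Proparacaine.
- 90% CI: (a − c) ± 1.672·√(2s²/30).
- Probability of a claim: the sum of the product of the two binomial probabilities over all outcome pairs that meet the rule.

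**Tipping point, Proparacaine at 29/30.**
- AG-920 26/30: s² = (3.467 + 0.967)/58 = 0.0764; SE = 0.0714; difference −0.100; 90% CI −0.219 to 0.019. The rule fails.
- AG-920 27/30: s² = (2.700 + 0.967)/58 = 0.0632; SE = 0.0649; difference −0.067; 90% CI −0.175 to 0.042. The rule is met, also with the margin at 20% of the reference rate (0.193).
- P > 0.05 is already met at AG-920 25/30.

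One answer therefore separates a claim from no claim on the CI rule.

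**Leniency towards AG-920, true 95% vs 75%.** About 30 × 0.25 = 7.5 AG-920 failures are expected, so L = 25% is about 2 children and L = 50% about 4.

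| L | q | CI within ±20 points | CI within 20% of reference rate | P > 0.05 |
|---|---|---|---|---|
| 0 | 0.750 | 7% | 5% | 37% |
| 25% | 0.8125 | 24% | 18% | 59% |
| 50% | 0.875 | 56% | 48% | 82% |

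**Other assumed rates, ±20-point CI rule, L = 0 / 25% / 50%.**
- True 90% vs 70%: 4%, 18%, 47%.
- True 95% vs 90% (q = 0.90, 0.925, 0.95): 71%, 84%, 92%.

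**Bias against AG-920.** True 95% in both arms, with 10% of AG-920 successes scored NO, gives q = 0.95 × 0.90 = 0.855. The chance of meeting the ±20-point rule falls from 92% to 44%.

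**Equal leniency in both arms, true 95% vs 75%.** With L = 25% or 50% in each arm, the ±20-point rule is met 21% or 51% of the time.

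**The case against.** Four points can be made on the other side.

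1. **No sentence says the investigator knows the arm.** A reader might infer that the documents state this outright. They do not. It follows from masking that covers the family only, a list held at the site and distinguishable containers, and under SAP 2.2 from the investigator giving the drops. The inference is strong, and neither document has any measure to keep the arm from the assessor. The objection changes the wording, not the point.

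2. **A reader might infer that the assessor can be masked at no cost because staff already dose.** Only the Protocol supports this, and it never says that the person dosing differs from the person assessing. SAP 2.2 says the opposite. The change needs that conflict resolved first. This objection stands.

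3. **A reader might infer that masking would remove all the inflation.** It would not. Equal leniency in both arms produces 21% and 51%, close to the 24% and 56% for AG-920 alone, and a masked assessor can still be generous to everyone. Masking is worth doing for the arm-dependent part only. This objection stands.

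4. **The rates and the direction of bias are assumed.** Both 20-point scenarios sit on the margin, and at 95% vs 90% the effect is smaller. Bias could also run against AG-920. With fair scoring, the 37% pass rate on P > 0.05 comes from the accept-the-null rule and not from masking. All of this is correct. The figures show sensitivity and do not predict the result.

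**Conclusion.** The concern holds in this form: one subjective answer, from an assessor neither document masks, is the whole efficacy evidence in a trial that succeeds by finding no difference. Arm-dependent scoring in either direction can decide the outcome, and bias in that answer cannot be repaired after the data are collected.

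Under the assumptions above, two to four AG-920 answers move the chance of a claim from 7% to between 24% and 56% at a true 20-point deficit. Bias the other way can halve the chance of a correct claim. These sizes depend on 30 per arm, on assumed rates and leniency shares, and on how the ±20% margin is read.

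The documents do not support saying that bias will occur, that it will favour AG-920, or that masking alone would make the scoring fair. The conflict over who doses is a separate inconsistency and must be resolved whatever is decided on masking.

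**What to change.** 1. **Reconcile the dosing passages.** Bring SAP 2.2 into line with Protocol 3.1 and section 5, and state that a staff member other than the assessor gives the drops.
2. **Mask the assessor.** Amend Protocol 3.2 and 3.5 and SAP 2.4 so that the person dosing holds the list and kit, doses out of the assessor's sight, removes the container and does not discuss the arm. The investigator who answers the adequacy question stays masked until the Day 1 assessment is signed. Write in emergency access to the code, since Protocol 3.5 currently sees no need for it.
3. **Check the mask.** Add a CRF item on whether the assessor knew or guessed the arm, and report it by arm. Treat any analysis that leaves out those children as exploratory only, because it excludes on an event after randomization that may differ between arms.

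Written criteria for an adequate exam would be a useful addition, because masking does not address a general tendency to answer YES.

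**Cost.** A short amendment to both documents, a site instruction and one CRF item. Dosing and assessment must be kept apart for a few minutes by staff already at the site. The documents give no staffing for the 1-3 sites, so each site should confirm that it has a second person available. The sample size, visits and assessments do not change.
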